Study drug will be dispensed at Day 0, Week 4, Week 8 and Week 12 visits (however, in the case of lost or damaged study drug, study drug can be dispensed at any study site visit). The subjects should bring their remaining study drug to each study visit. At Study Visits Week 4 (or Week 6 if applicable) and Week 12, subjects participating in the PK assessments should be instructed to not take their study drug dose at home (it will be administered at the site). At Weeks 4, 8, and 12, subjects will return study drug and will be dispensed new bottles. At Week 2 and 6, subjects will bring their drug supply to the study site to allow site personnel to perform a pill count; however, no new study drug will be dispensed at these visits.

Week 16 Visit

Subjects will take their last dose of study drug at home and come to the study site to undergo a clinical evaluation, including a review of any changes to medical (including cardiac) conditions and medications/other therapies, and a complete physical exam, which will include measurements of weight and vital signs. An ECG will also be performed for safety monitoring. In addition, subjects will have blood and urine samples obtained for safety labs. Blood samples will also be obtained for RNA expression and soluble serum biomarker assessments. In addition,

a mid-turbinate nasal swab will be obtained. Subjects will be queried by site staff regarding any visits to ER, urgent care clinics, any admission to a skilled nursing facility or hospital that may have occurred since their last study visit. All subjects will complete the EQ-5D-5L questionnaire at the Week 16 visit. All study drugs (RTB101 and placebo) should be returned to the study site.

Short-term Follow-up Period (Week 20)

All subjects will return to the study site 4 weeks after their last dose of study drug for a Week 20 (Short-term Follow-up Period) visit. At the Week 20 visit, subjects will undergo a complete physical exam, which will include measurements of weight and vital signs. A review of any changes to medical (including cardiac) conditions and medications or other therapies will also be performed. Blood and urine will be collected for safety lab evaluation. The eDiary should also be returned to site personnel at this visit.

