An exploratory endpoint will be the rate of viral respiratory infection, irrespective of whether the infection is symptomatic, to better assess the antiviral effects of RTB101. As an additional exploratory endpoint, healthcare resource utilization will be assessed because an important benefit of decreasing the incidence of clinically symptomatic respiratory illness may be a decrease in healthcare resource utilization by elderly subjects. Since decreasing the incidence of clinically symptomatic respiratory illness may improve the quality of life of elderly subjects, an

additional exploratory endpoint will be health related quality of life in all subjects assessed with the EQ-5D-5L questionnaire. The incidence of clinically symptomatic respiratory illness in subjects with a medical history of asthma or who are ≥ 85 years of age will be assessed as exploratory endpoints because these subpopulations had the greatest reduction on the incidence of laboratory confirmed RTIs after treatment with 10 mg RTB101 once daily as compared with placebo in the previous Phase 2b (RTB-BEZ235-202) trial. The incidence of asthma exacerbations in subjects with a medical history of asthma will also be assessed since RTIs are common causes of asthma exacerbations. Another exploratory endpoint will be the incidence of clinically symptomatic respiratory illness and the incidence of symptomatic respiratory illness associated with laboratory-confirmed pathogen(s) through Week 20 to assess if the efficacy of RTB101 persists for 4 weeks after subjects discontinue study drug. To better understand if the incidence of other types of infections may be reduced, the incidence of UTIs will be assessed. Finally, RNA expression and soluble serum biomarkers and pharmacogenomics (also known as pharmacogenetics) (Note: pharmacogenomics will only be assessed in those subjects who sign a separate consent form to allow collection of a pharmacogenomic (also known as pharmacogenetic) sample) will be assessed as exploratory endpoints to assess the effects of RTB101 on relevant immunologic markers and to potentially assess the impact of mTOR pathway polymorphisms in a pharmacogenomic analysis.

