3.3. Exploratory Objectives

The exploratory objectives are:

- To explore the effect of RTB101 as compared to placebo on the rate of all laboratory-confirmed viral respiratory infections with or without symptoms through Week 16
- To explore the effect of RTB101 as compared to placebo on the rate of all-cause hospitalizations through Week 16
- To explore the effect of RTB101 as compared to placebo on the rate of hospitalizations associated with RTIs through Week 16
- To explore the effect of RTB101 as compared to placebo on the rate of all-cause Emergency Room (ER) visits through Week 16

This document is confidential.

- To explore the effect of RTB101 as compared to placebo on the rate of ER visits associated with RTIs through Week 16
- To explore the effect of RTB101 as compared to placebo on the rate of all-cause urgent care clinic visits through Week 16
- To explore the effect of RTB101 as compared to placebo on the rate of all urgent care clinic visits for clinically symptomatic respiratory illness through Week 16
- To explore the effect of RTB101 as compared to placebo on the rate of all-cause admissions to skilled nursing facilities through Week 16
- To explore the effect of RTB101 as compared to placebo on hospital length of stay associated with RTIs through Week 16
- To explore the effect of RTB101 as compared to placebo on all-cause hospital length of stay through Week 16
- To explore the effect of RTB101 as compared to placebo on the percentage of subjects with clinically symptomatic respiratory illness and the percentage of subjects with clinically symptomatic respiratory illness associated with ≥ 1 laboratory-confirmed pathogen(s) through Week 20
- To explore the effect of RTB101 as compared to placebo on change from Baseline in health-related quality of life (HRQoL) as assessed by EQ-5D-5L scores during all clinically symptomatic respiratory illness episodes and at Week 16
- To explore the effect of RTB101 as compared to placebo on the percentage of subjects with clinically symptomatic respiratory illnesses and on the percentage of subjects with clinically symptomatic respiratory illnesses associated with ≥ 1 laboratory-confirmed pathogen(s) through Week 16 who are ≥ 85 years of age or subjects with a medical history of asthma

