A separate CSRI event will not be diagnosed until a subject has ≥ 7 consecutive days during which all CSRI-defining symptoms are reported as “Absent” after the end date of the prior CSRI episode. If missing days of eDiary entries are sandwiched between 2 days of eDiary entries during which all CSRI-defining symptoms are reported as “Absent”, then all symptoms will also be considered as “Absent” for the missing eDiary entries, and a separate CSRI event can be diagnosed if the ≥ 7 consecutive days criterion is met. For example, if on Day 4 and Day 10 all symptoms were reported as “Absent” in the eDiary, and on Days 5-9 the eDiary entries were missing, then all symptoms will be considered as “Absent” on Days 5-9. Therefore all symptoms will be considered as “Absent” for 7 consecutive days (Days 4-10), and a separate CSRI can be diagnosed.

Only CSRI events having a start date at least 3 days after the start of study drug and meet the definition of a CSRI by the specified time point (Week 16 or Week 20) will be included in the analysis. Only data recorded in the eDiary through the evening before the Week 16 visit will be included in all analyses of CSRI events for the Week 16 endpoint. Similarly, only data recorded in the eDiary through the evening before the Week 20 visit will be included in all analyses of CSRI events for the Week 20 endpoint.

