9.1. Multiple Testing Strategy

A fixed sequence gate-keeping strategy will be used to control the study-wise error rate at a 2-sided α -level of 0.05. The following primary, secondary and exploratory efficacy endpoints will be tested in the sequence specified below:

Order	
H₁	The percentage of subjects with 1 or more CSRIs (with or without an associated laboratory-confirmed pathogen) beginning at least 3 days after the start of study drug treatment through Week 16.
H₂	The percentage of subjects with 1 or more CSRIs associated with ≥ 1 laboratory-confirmed pathogen(s) beginning at least 3 days after the start of study drug treatment through Week 16 as assessed by pre-specified clinical diagnostic criteria, and respiratory pathogen PCR of nasopharyngeal swabs, sputum gram stain and culture, and/or RIDTs.
H₃	The rate of CSRI (with or without an associated laboratory-confirmed pathogen) beginning at least 3 days after the start of study drug treatment through Week 16 as assessed by pre-specified clinical diagnostic criteria.
H₄	The rate of CSRIs associated with ≥ 1 laboratory-confirmed pathogen(s) beginning at least 3 days after the start of study drug treatment through Week 16 as assessed by pre-specified clinical diagnostic criteria and respiratory pathogen PCR of nasopharyngeal swabs, sputum gram stain and culture, and/or RIDTs.
H₅	The time to alleviation of moderate and severe respiratory illness symptoms due to CSRI beginning at least 3 days after the start of study drug treatment through Week 16.
H₆	The percentage of subjects with severe symptoms due to CSRIs beginning at least 3 days after the start of study drug treatment through Week 16.
H₇	The rate of all-cause hospitalizations beginning at least 3 days after the start of study drug treatment through Week 16.
H₈	The rate of UTIs beginning at least 3 days after the start of study drug treatment through Week 16 reported as adverse events
H₉	The percentage of subjects with 1 or more CSRIs (with or without an associated laboratory-confirmed pathogen) beginning at least 3 days after the start of study drug treatment through Week 20.

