A generalized linear model analysis will be conducted using the number of CSRI per 16-week period (illnesses/16 weeks) as the dependent variable and will include treatment group, age (continuous covariate), Clinical Frailty Scale score (ordinal covariate), medical history of diabetes mellitus type 2 (Y/N), medical history of asthma (Y/N) medical history of CHF (Y/N), and receipt of current season influenza vaccination (Y/N) as fixed effects.

This document is confidential.

The rate ratio (RR) (RTB101 dose group to placebo) of the treatment effect will be derived from the model along with the 95% 2-sided confidence interval (CI). Model-adjusted mean rates for each treatment group and their corresponding 95% 2-sided CI will also be calculated.

The “log” link function will be used in the model and an offset term will be included to account for variable lengths of treatment exposure across the subjects. The unadjusted rate of CSRI per subject through Week 16 will be calculated by summing the number of total CSRIs per subject through Week 16 within each treatment group.

Analysis of this endpoint will be based on the estimand for the secondary objective corresponding to this endpoint described in 9.2.2 above.

Summary statistics will be presented along with a full data listing by treatment group.

9.4.3. Rate of Clinically Symptomatic Respiratory Illness Associated with ≥ 1 Laboratory-confirmed Pathogen(s)

The rate of CSRIs associated with ≥ 1 laboratory-confirmed pathogen(s) beginning at least 3 days after the start of study drug treatment through Week 16 (**H₄**) as assessed by pre-specified clinical diagnostic criteria and respiratory pathogen PCR of nasopharyngeal swabs, sputum gram stain and culture, and/or RIDTs will be analyzed in the same manner as described in 9.4.2 above, based on the estimand for the secondary objective corresponding to this endpoint described in 9.2.2 above. Section 9.4.1 describes which laboratory result will be used to determine if the CSRI is associated with ≥ 1 laboratory-confirmed pathogen.

Summary statistics will be presented along with a full data listing by treatment group.

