9.5.9. Hospitalization Length of Stay Associated with RTIs

Total hospitalization length of stay associated with RTIs beginning at least 3 days after the start of study drug treatment through Week 16 will be analyzed as an exploratory endpoint.

Total hospitalization length of stay associated with RTIs will consist of the total duration of hospitalizations associated with RTIs for each subject starting between 3 days after the start of study drug and prior to Week 16. Duration of a hospital stay is defined as (hospital discharge date – hospital admission date) +1.

The analysis will be performed using the Analysis of Covariance model (PROC MIXED) with fixed effects for treatment group, age (continuous covariate), Clinical Frailty Scale score (ordinal covariate), medical history of diabetes mellitus type 2 (Y/N), medical history of asthma (Y/N), medical history of CHF (Y/N), and receipt of current season influenza vaccination (Y/N) as covariates. The least squares (LS) means, differences between LS means, a 95% 2-sided CLs for the difference and the p-values from model effects will be reported for overall treatment to evaluate the treatment effect.

Summary statistics, including Least Squares Mean and standard error for each treatment and the treatment difference will be presented along with a full data listing by treatment group.

9.5.10. Percentage of Subjects with 1 or more Clinically Symptomatic Respiratory Illnesses (with or without an Associated Laboratory-confirmed Pathogen) through Week 20

The percentage of subjects with 1 or more CSRIs (with or without an associated laboratory-confirmed pathogen) beginning at least 3 days after the start of study drug treatment through Week 20 (**H₉**) will be analyzed in the same manner as the primary efficacy analysis as described in [9.3.1 above](#).

Summary statistics will be presented along with a full data listing by treatment group.

9.5.11. Percentage of Subjects with 1 or more Clinically Symptomatic Respiratory Illnesses Associated with ≥ 1 Laboratory-confirmed Pathogen(s) through Week 20

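### The Week 20 CSRI endpoint (H9) counts illnesses from 3 days after first dose, so by itself it shows cumulative benefit and not the off-drug persistence that a clause in Protocol 3.2 suggests

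*Protocol*

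**What the plan says.** In its paragraph on exploratory endpoints, Protocol 3.2 says CSRI incidence, overall and laboratory-confirmed, is assessed "through Week 20 to assess if the efficacy of RTB101 persists for 4 weeks after subjects discontinue study drug".

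The operational text is cumulative throughout:

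- SAP 9.1, like Protocol 9.4.1, defines H9 as the percentage of subjects with a CSRI "beginning at least 3 days after the start of study drug treatment through Week 20".
- SAP 9.5.10 (body numbering; the contents list has it as 9.5.11) analyses "The percentage of subjects with 1 or more CSRIs (with or without an associated laboratory-confirmed pathogen) beginning at least 3 days" after first dose through Week 20, with the same logistic regression as the primary endpoint.
- SAP 7.2.1 gives the Week 16 and Week 20 endpoints the same start point. Only the end differs. For Week 16 the cut is explicit: "Only data recorded in the eDiary through the evening before the Week 16 visit will be included".

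The formal objective is neutral. SAP 3.3 refers only to CSRI and to "clinically symptomatic respiratory illness associated with ≥ 1 laboratory-confirmed pathogen(s) through Week 20", with no mention of persistence.

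Dosing runs to the Week 16 visit day: "Subjects will take their last dose of study drug at home and come to the study site". No analysis in SAP 9.5, SAP 9.6 or the table index isolates Weeks 16–20.

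Protocol 1.2.2 meets the same issue in Phase 2b. It calls the cumulative 24-week result a persistent benefit, then says the 16 treated weeks may have driven it because few laboratory-confirmed RTIs came later.

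**The concern.** On its natural reading, the rationale clause asks whether protection continues once the drug is stopped. H9 answers a different question: whether fewer RTB101 subjects have had any CSRI by Week 20. Most of those illnesses will have started during the 16 treatment weeks, so a real on-drug effect can carry H9 to significance even if protection ends with the last dose.

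H9 sits in the alpha-controlled sequence, so a success there would be a formal finding. Read alongside the clause, it could be reported as persistence off drug. The caveat in Protocol 1.2.2 is not carried over to H9.

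**Working it through.** **Plan's own figure.** Inputs from Protocol 9.6: 28.2% versus 19.7%, 533 per arm, two-sided 0.05, likelihood-ratio chi-square. Power is 90.3%. With an exact 30% reduction (0.70 × 28.2% = 19.74%) it is 90.0%, and 533 per arm gives 1066. The stated 90% reproduces.

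**Assumed Weeks 16–20 risk.** The documents give none. I use two placebo values for subjects still illness-free at Week 16: 4%, and the constant-hazard value 1 − (1 − 0.282)^(1/4) = 7.9%.

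**Share of H9 cases already present at Week 16, no off-drug effect.** With Week 16 risk p and later risk q, the share is p / [p + (1 − p)q].

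- At 4%: placebo 0.282 / (0.282 + 0.718 × 0.04) = 91%; RTB101 0.197 / (0.197 + 0.803 × 0.04) = 86%.
- At 7.9%: 83% and 76%.

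**How often H9 is significant in favour of RTB101.** I simulated 400,000 trials per scenario: binomial events to Week 16, then binomial first events in illness-free subjects, with an unadjusted likelihood-ratio chi-square. Full persistence is modelled as the on-drug hazard ratio, ln(0.803)/ln(0.718) = 0.662, or as the on-drug risk ratio, 0.70. H2 to H8 are ignored.

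| RTB101 in Weeks 16–20 | 4%: all trials | 4%: H1 significant | 7.9%: all trials | 7.9%: H1 significant |
|---|---|---|---|---|
| No off-drug effect | 85% | 93% | 80% | 87% |
| Full persistence, hazard ratio 0.662 | 93% | 99% | 95% | 99% |
| Full persistence, risk ratio 0.70 | 92% | 98% | 94% | 98% |
| Hazard 1.5 times placebo | 67% | – | 40% | – |
| Risk twice placebo | 43% | – | 7% | – |

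With doubled risk, H9 is significant against RTB101 in under 1% of trials at either placebo risk.

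**Sensitivity to the on-drug effect.** With a 20% reduction (28.2% versus 22.56%), H9 is significant in 50% (4%) or 45% (7.9%) of trials with no off-drug effect, and in 59–60% or 62–64% with persistence. Across both effect sizes the two states differ by about 7 to 19 percentage points.

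**What a separate Weeks 16–20 estimate could give.** Taking all 533 per arm, expected placebo events are 533 × 0.04 = 21.3 to 533 × 0.0795 = 42.4. At a ratio of 0.70, RTB101 has 14.9 to 29.7. The 95% interval is 0.70 × exp(±1.96 × √(1/a + 1/b)), where a and b are the two event counts. This gives 0.36 to 1.36 at 4% and 0.44 to 1.12 at 7.9%. Power under full persistence is about 19% to 41%.

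**The case against.** The best defence is the protocol's own usage. Protocol 1.2.2 applies the word persistent to a cumulative result that it concedes may come from the treated weeks. If the Protocol 3.2 clause means retained net benefit, then clause, objective, endpoint and test all agree. This stands in part: a reader might infer that the protocol contradicts itself outright, and the documents do not support that. They leave the clause open to two readings, one of which H9 cannot serve.

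The harm is also a possible misreport, not a planned analysis. H9 is exploratory, last of nine, and formally tested only if H1 to H8 all succeed. That limits severity but does not make the label accurate.

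The Week 16 and Week 20 tables can be read together, so H9 is not the only information available. That is true, and significance alone understates what the outputs show. But the comparison yields only a crude first-illness risk in subjects illness-free at Week 16 (expected 533 × 0.718 = 383 and 533 × 0.803 = 428). It conditions on a post-randomisation outcome, omits repeat illnesses and has no planned interval.

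A reader might also infer that H9 would expose a rebound after stopping. It would not. A doubled risk often removes significance, but it almost never produces a significant result against RTB101, and a non-significant H9 does not identify a rebound.

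Finally, a Weeks 16–20 table will be imprecise. That is correct, and it is why the table should be descriptive only.

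**Conclusion.** The point holds at minor severity. H9 is a valid test of cumulative benefit through Week 20. A reader might infer that its type I error is compromised, but for the hypothesis it states it is not, and no primary or secondary conclusion changes. What fails is the step from a significant H9 to persistence off drug, because H9 is significant in most trials at the planned effect whether or not any off-drug effect exists.

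The percentages rest on the planned Week 16 rates, on the assumed 4% and 7.9% risks, on an unadjusted test, and on treating illness to Week 16 as on-drug, although some subjects will stop early. The structural conclusion does not depend on them: the counting window includes the treatment period.

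**What to change.** 1. Reword the Protocol 3.2 clause to say that incidence through Week 20 assesses cumulative benefit through Week 20. State in SAP 9.5.10 and 9.5.11 (body numbering) that these results alone are not evidence of off-drug persistence.

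2. Add one descriptive table by randomised arm, outside the alpha sequence. Count new CSRIs that start after the Week 16 cut, through the Week 20 cut, in FAS subjects with eDiary follow-up in that period.
   - Give counts, time at risk, and a rate ratio with 95% CI from a Poisson model with robust variance, unadjusted or with few covariates. The covariate-adjusted negative binomial model of SAP 9.4.2 is poorly suited to about 36 to 72 mostly single events.
   - Use eDiary time at risk after the cut. The SAP 9.4.2 offset does not apply off drug: "an offset term will be included to account for variable lengths of treatment exposure across the subjects".
   - Leave out days on which no new event can be diagnosed under SAP 7.2.1: "A separate CSRI event will not be diagnosed until a subject has ≥ 7 consecutive days during which all CSRI-defining symptoms are reported" as absent. This is a small correction: with an assumed 17 to 21 blocked days per illness it moves the ratio by less than 1%.
   - Repeat the table counting only CSRIs that start at least 3 days after the last dose. This matches the incubation argument that Protocol 3.2 uses at the start of treatment.

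The cost is one protocol clause, two SAP sentences and one table from eDiary data already collected through Week 20. The table will seldom settle the question. Subjects followed past Week 16 are a post-randomisation subset, and the SAP should say that a null result is not evidence of no persistence.

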3.2.1. Rationale for Choice of Comparator

A placebo will be used as a comparator since there is no available drug known to reduce the incidence of clinically symptomatic respiratory illness in the elderly. The placebo arm will provide data about baseline AE and clinically symptomatic respiratory illness incidence in the elderly to which responses in subjects receiving RTB101 can be compared.

3.3. Risks and Benefits

The potential benefit to subjects receiving RTB101 of reducing the incidence of clinically symptomatic respiratory illness is noted above. The potential risk to subjects in this study will be minimized by adherence to the inclusion/exclusion criteria, close clinical monitoring, short study duration, and oversight by a DMC. The potential risks of RTB101 treatment are based on preclinical toxicology studies, and the observed safety of RTB101 in clinical trials to date. As noted above, the risk of AEs should also be minimized in this study by using very low doses of RTB101. The dose of RTB101 to be used in the proposed Phase 3 trial (10 mg once daily) is 120-fold lower than the maximum tolerated dose (1200 mg once daily) established in humans. The RTB101 10 mg once daily dose was also demonstrated to be safe and well tolerated in elderly subjects in 2 studies: 1) a previous Phase 2a study in which 53 elderly subjects were

treated with 10 mg once daily for up to 6 weeks, and 2) a previous Phase 2b study in which 176 elderly subjects were exposed to 10 mg once daily for up to 16 weeks. Thus, the nonclinical and clinical safety data supports the safety of the proposed Phase 3 clinical trial dose of RTB101 (10 mg once daily) in elderly subjects. However, RTB101-associated AEs seen when RTB101 has been used at significantly higher doses in oncology studies still represent potential risks as described below.

Stomatitis/Mucositis

Mouth ulcers/stomatitis similar to canker sores are common AEs following treatment with high doses of RTB101 in oncology studies. No increase in the incidence of mouth ulcers/stomatitis was observed in elderly subjects treated with RTB101 10 mg once daily as compared to placebo in the Phase 2a clinical trial CBEZ235Y2201 and the Phase 2b clinical trial RTB-BEZ235-202. However, in CBEZ235Y2201, one subject in the 10 mg RTB101 once daily dosing group discontinued study drug treatment due to mouth ulcers of moderate severity.

If needed, topical treatments are recommended, but alcohol- or peroxide-containing mouthwashes should be avoided as they may exacerbate the condition. Antifungal agents should not be used unless fungal infection has been diagnosed.

Gastrointestinal Symptoms

Gastrointestinal symptoms including nausea, vomiting, and diarrhea are common AEs following treatment with high doses of RTB101 in oncology studies.

During the one year of study follow-up of elderly subjects in the Phase 2a clinical trial CBEZ235Y2201, diarrhea occurred in:

- 8% of subjects in the placebo treatment group
- 19% of subjects in the RTB101 10 mg once daily treatment group

During the 24 weeks of study follow-up of elderly subjects in the Phase 2b clinical trial RTB-BEZ235-202, diarrhea occurred in:

- 4.4% of subjects in the placebo treatment group
- 4.5% of subjects in the RTB101 10 mg once daily treatment group

No increase in the incidence of nausea or vomiting was observed in elderly subjects treated with RTB101 10 mg once daily as compared to placebo in clinical trials CBEZ235Y2201 and RTB-

BEZ235-202, however in CBEZ235Y2201, one subject in the RTB101 10 mg treatment group discontinued study drug due to nausea.

In Study RTB-101-204, subjects must be monitored for signs of gastrointestinal irritation. Subjects experiencing nausea, vomiting, or diarrhea should receive appropriate medical treatment. Study drug should be permanently discontinued if a subject develops a gastrointestinal SAE, such as gastrointestinal bleeding or perforation. Study drug should also be permanently discontinued if a subject develops oral ulcers, stomatitis, or diarrhea that limits oral intake or is associated with dehydration or weight loss (>2% Baseline weight) over 2 or more consecutive study visits (see [Section 5.5.2](#)).

Fatigue

Fatigue/asthenia has been commonly reported following treatment with high doses of RTB101 in oncology studies. The incidence of fatigue was similar in the RTB101 10 mg once daily and placebo arms in elderly subjects in clinical trials CBEZ235Y2201 and RTB-BEZ235-202.

Rash

Rash has been frequently reported following treatment with high doses of RTB101 in oncology studies.

During the one year of study follow-up of elderly subjects in the Phase 2a clinical trial CBEZ25Y2201, rash occurred in:

- 3.8% of subjects in the placebo treatment group
- 3.8% of subjects in the RTB101 10 mg once daily treatment group

During the 24 weeks of study follow-up of elderly subjects in clinical trial RTB-BEZ235-202, rash occurred in:

- 2.2% of subjects in the placebo treatment group
- 0.6% of subjects in the RTB101 10 mg once daily treatment group

Subjects that experience rash while receiving RTB101 should receive appropriate symptomatic treatment.

Hyperglycemia

Hyperglycemia has commonly been seen following treatment with high dose RTB101 in oncology clinical trials. The incidence of hyperglycemia was similar in the RTB101 10 mg once daily and placebo arms in clinical trials CBEZ235Y2201 and RTB-BEZ235-202. Blood glucose levels will be closely monitored throughout the current trial.

Hematopoietic and Lymphopoietic Systems

Anemia, leukopenia and thrombocytopenia are common AEs following treatment with high doses of RTB101 in oncology studies. No increase in the incidence of anemia, leukopenia or thrombocytopenia was observed in elderly subjects treated with RTB101 10 mg once daily as compared to placebo in clinical trials CBEZ235Y2201 and RTB-BEZ235-202. Complete blood counts will be followed at each visit while subjects are on study drug.

Lipid Abnormalities

Lipid disturbances are common in clinical trials of the rapalog class of mTOR inhibitors but are uncommon in clinical trials of RTB101. The incidence of hyperlipidemia was similar in the RTB101 10 mg once daily and placebo arms in elderly subjects in clinical trials CBEZ235Y2201 and RTB-BEZ235-202. Cholesterol and triglyceride levels will be followed at each visit.

Cardiovascular Events

Preclinical findings did not indicate prominent cardiac risks of RTB101. In clinical studies with high doses of RTB101 in oncology subjects, only few cases of cardiac AEs were reported, and it is not clear if RTB101 increases the risk of cardiac events. A suspected case of myocardial infarction (MI) was reported in an oncology subject treated with high dose RTB101 (200 mg bid) in combination with everolimus, and a suspected case of acute coronary syndrome was reported in an oncology subject receiving high dose RTB101 in combination with paclitaxel. No increase in the incidence of cardiac events was observed in elderly subjects treated with RTB101 10 mg once daily as compared to placebo in clinical trial CBEZ235Y2201. In RTB-BEZ235-202, 3 elderly subjects with multiple cardiac risk factors had a MI in the RTB101 5 mg once daily treatment arm. No MIs occurred in the RTB101 10 mg once daily, RTB101 10 mg twice daily, RTB101 10 mg + everolimus or placebo treatment arms. Nevertheless, subjects with active severe, uncontrolled and/or unstable cardiac conditions (including subjects with unstable angina pectoris or acute ischemic changes on ECG at Screening or Baseline [see [Section 4.2](#)]) will be excluded from Study RTB-101-204. Central analysis of ECG data in oncology study CBEZ235A2101 did not show any evidence for QT prolongation. A preliminary exposure-QT analysis showed no significant impact of RTB101 plasma concentration on QT interval. Despite

these findings, as a conservative measure, subjects with a QTcF >480 msec at Screening or Baseline will also be excluded from study participation (see [Section 4.2](#)).

From the Baseline through the Week 20 Visit (i.e., completion of the Short-term Follow-up Period) in Study RTB-101-204, subjects will be queried with regard to any new cardiac symptoms (see SOM for details); a cardiac exam will be performed as part of required complete and targeted physical examinations (see [Table 6-1](#) [Assessment Schedule]), and ECGs will be obtained at the Week 4, Week 8, Week 12, and Week 16 visits post-Baseline. Any QTcF >500 msec or >60 msec QTcF change from a subject's Baseline ECG, or any other clinically significant abnormal ECG change should be reported as an AE. As a safety precaution, subjects experiencing any cardiac-related SAEs (including, but not limited to, MI and unstable angina) must permanently discontinue study drug treatment (see [Section 5.5.2](#)).

Liver Toxicity

Elevated liver function tests (LFTs) have been reported in oncology subjects treated with high dose RTB101. No increase in the incidence of elevated LFTs was observed in elderly subjects treated with RTB101 10 mg once daily as compared to placebo in clinical trials CBEZ235Y2201 and RTB-BEZ235-202. However, subjects with active hepatitis or with significant LFT elevations should be excluded from this RTB101 trial. An elevation of alanine aminotransferase (ALT), aspartate aminotransferase (AST) or total bilirubin >3 x ULN should be reported as a severe (Common Terminology Criteria for Adverse Events [CTCAE] Grade 3) AE.

Pneumonitis

Non-infectious pneumonitis is a class effect of mTOR inhibitors that are rapamycin-derivatives. However, it is unclear if RTB101 is associated with an increased risk of interstitial pneumonitis even when administered at high doses. In clinical trials of high dose RTB101 in 442 advanced cancer subjects, 5 cases of interstitial pneumonitis potentially related to RTB101 have been reported. However, 2 of these subjects were also receiving rapamycin-derivatives, and two had underlying pneumonia. No elderly subjects developed pneumonitis while receiving low dose RTB101 in clinical studies CBEZ235Y2201 or RTB-BEZ235-202.

Consider a diagnosis of non-infectious pneumonitis in subjects presenting with non-specific respiratory signs and symptoms such as hypoxia, pleural effusion, cough, or dyspnea, and in whom infectious, neoplastic, and other causes have been excluded by means of appropriate investigations. The lung toxicity has been reported to be completely reversible in most of the cases upon drug interruption or discontinuation. The use of corticosteroids may be indicated. See [Section 13.2](#) (Appendix 2) for an algorithm for treating interstitial pneumonitis.

4. Population

The study population will be comprised of elderly individuals ≥ 65 years of age without unstable underlying medical conditions defined as conditions that require acute medical intervention or ongoing adjustments of concomitant medications (as determined by medical history, ECG and laboratory tests at Screening, and physical examination, ECG and vital signs at Screening and Baseline). The goal is to randomize approximately 1066 subjects during winter cold and flu season.

The Investigator must ensure that all patients being considered for the study meet the following eligibility criteria. No additional criteria should be applied by the Investigator so that the study population will be representative of all eligible subjects. Subject selection is to be established by checking through inclusion/exclusion criteria at Screening and Baseline. A relevant record (e.g., checklist) of the eligibility criteria must be stored with the source documentation at the study site. Deviation from **any** entry criterion excludes a subject from enrollment into the study.

